2.4 Wisepill/Wisebag Technology

Wisebag™ (Wisepill Technologies Adherence Management Solutions, South Africa) is a portable, lunch-bag size container, which can contain approximately 30 individually wrapped gel applicators or more, closes with a zipper, and has a self-contained battery-operated electronic device that includes a chip which provides an electronic signal each time an opening event occurs, and counts and records any opening events, as well as a daily control signal ('heart beat') to signify proper battery functioning. Wisebag event monitoring system can be set-up such that all data are stored in the device until the information is downloaded at the clinic at follow-up visits (offline modality) or, each time an event occurs, a signal is sent to the central management system in real-time through a wireless system (online modality). Through this latter modality, it is possible to monitor adherence on an ongoing, 'real time' basis. The real time data capture and monitoring, although more expensive, allows up to the minute insight on patterns of use and non-use as well as the ability, where appropriate, to follow up with participants when non-adherent.

In recent HIV treatment studies, as described above, the Wisepill, a similar device using wireless technology to monitor tablet use, has allowed assessment of tablet-taking opening events in real time, and in combination with cell-phone reminders.^[15] In another recent study, Wisebag was piloted among 10 participants in the CAPRISA 004 trial, and this was the first application of such a technology to the microbicide context^[11]. Another pilot study currently being conducted in Uganda among 50 caretaker/infant pairs is using Wisebag for pediatric liquid HIV treatment in Uganda ([name], personal communication).

Like Wisepill and MEMS caps, the Wisebag electronic device monitors each opening event of the bag, and provides a date and time stamp of when these occurred. This non-invasive indirect objective approach to monitor adherence, has thus been adapted to monitor gel applicator use.

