2.5 Wisebag Pilot Study

Wisebag Pretest Phase

Wisebag will first go through a pretest phase in the US and at a selected study site, with members of the research team, prior to implantation of the Wisebag pilot study. The pretest activities will include:

- Pre-testing the offline functionality and performance of Wisebag in a “controlled” setting;
- Adapt an algorithm for identifying “curiosity events” (i.e. openings without taking any products);
- Monitor the temperature level inside the Wisebag under different ambient temperature conditions anticipated at the study site;
- Develop and pretest with staff the educational materials and instruction sheets, to ensure it is suitable for use in sub-Saharan Africa.

Wisebag Pilot Study

The overall goal of this pilot study is to determine if Wisebag is suitable for use in sub-Saharan Africa and to assess its utility in providing adherence monitoring data among women who present and screen for participation in a HIV prevention trial. Findings from this Wisebag pilot study will help determine the feasibility of including Wisebag in the final design of a larger VOICE ancillary study of objective measures of adherence. Considerations for using an electronic events monitoring systems (EMS) for the vaginal group in VOICE include:

- a) the current absence of any validated biomarkers as surrogates of vaginal gel adherence;
- b) the provision of a noninvasive indirect objective measure of applicator use that can accurately measure opening events from an applicator storage bag, and;
- c) the potential relative logistical simplicity of deploying this monitoring tool at a subset of VOICE sites.

This new technology may provide critically needed information to VOICE investigators in order to understand pattern of use and adherence levels of the vaginal gel among VOICE vaginal group participants.

In summary, this Wisebag pilot is a randomized pilot study (1:2:2 ratio) assessing three Wisebag functionalities (‘dummy’, online and offline), described herein. Approximately 50 HIV-uninfected women, who screen out of VOICE for administrative, clinical or laboratory reasons,

will be enrolled at one or more sites in sub-Saharan Africa, as designated by the MTN EC Committee.

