4 STUDY DESIGN

4.1 Identification of Study Design

MTN-003-P01 is a three-arm, randomized, placebo-controlled, double-blinded pilot study of Wisebag for monitoring daily product use. The study is double-blinded with respect to participants and investigators, (but not for pharmacy and information technology (IT) staff who will manage the download of the electronic data and the battery charging of Wisebag devices). Approximately 50 participants will be randomized to the 3 study arms in a 1:2:2 ratio. The 3 groups will be “dummy” Wisebag (n~10) “Online device” Wisebag (n~20), or “Offline device” Wisebag (n~20).

There will be two study visits: an enrollment visit and one follow-up/exit visit, two weeks after enrollment. During study participation, participants will be asked to open their assigned Wisebag at approximately the same specified time daily, to peel off one sticker from a set of study stickers inside the bag, and place the sticker on the appropriate day of the week on a study provided diary card. After two weeks of daily openings, participants will be asked to return to the study clinic for an exit visit with their Wisebag and diary card.

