7.1 Screening and Enrollment

The Screening and Enrollment Visit for the Wisebag pilot should take place within approximately 4 weeks of the last VOICE Screening Visit; however participants may be enrolled up to 90 days after the date of the last VOICE Screening Visit. Screening for all data collection activities will include oral or written confirmation that participants meet the inclusion and exclusion criteria. Study staff will create checklists to ensure this is consistently documented.

Table 1: Screening and Enrollment

Screening and Enrollment	
Component	Procedures
Administrative and Regulatory	
 • Obtain informed consent • Confirm eligibility • Obtain locator information • Randomization • Schedule next (exit) visit • Provide counseling regarding protocol adherence • Provide reimbursement for study visit
Behavioral	
 • Conduct demographic and brief behavioral assessment • Dispense (2) weekly diary cards as well as the Wisebag along with instructions on use. • Practice opening/closing the bag and placing a study sticker on their diary card

7.2 Exit Visit: End of Week 2

Visit window at target exit visit date: The target visit exit date will be 2 weeks (14 days) from the enrolment date, with an allowable visit window of plus or minus 3 days. Participants who present late for their exit visit (Day 18 or later) will complete study procedures, as long as the study is still in the accrual phase. Otherwise, the participant will be classified as lost to follow up if they missed the exit visit window and there were 3 unsuccessful contact attempts.

Table 2: Exit Visit: End of Week 2

Week 3	
Component	Procedures
Administrative and Regulatory	
 • Collect Wisebag from participant. • Download data from the 2 week period from all “active” Wisebags • Provide reimbursement for study visit • Debrief on the full purpose of the research
Behavioral	
 • Conduct behavioral and acceptability assessment • Collect and review diary card • Semi-structured brief qualitative interview • Perceived Wisebag product

7.3 Interim Visits:

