10.5.2 Data Analysis

Performance endpoint

Performance will be assessed by comparing the number of failures (e.g., difficulties downloading stored data or receiving wireless data, battery- or signal-failures) experienced in each of the active-device groups. Questionnaire data reporting participants' user-related problems with the bag, device and/or battery will be tabulated overall and by randomization assignment. As indicated by the distribution of data, count data may be recoded and analyzed as categorical data. Count data will be compared using Poisson regression while categorical data will be compared using Chi-square tests. In cases of skewed data, alternative regression models may be implemented as appropriate.

Ability to Identify Randomization Arm

To assess blinding, the proportion of participants who are able to accurately identify whether they were randomized to the "dummy" or active-device groups will be reported. The proportion of participants who are able to indicate whether a demonstration bag is "dummy" or active (note that offline and online devices are identical, aside from the SIM card inside the online device), upon visual inspection, will also be reported. A summary statistic, such as the Cohen's kappa coefficient, will be used to summarize a) the level of agreement between the participant's response and the true group assignment and b) the level of agreement between the participant's response and the true bag type.

Concordance endpoint

Concordance between signal data and diary data will be summarized for participants assigned to the active device groups, and analysis will include the following: the proportion of participants whose number of events per signal data equals, exceeds, or is lower than the number of events per diary data. No formal testing will be performed on this endpoint.

Feasibility and acceptability endpoint

Feasibility and acceptability data collected at study exit by questionnaires will be summarized overall and by randomization group. No formal testing will be performed on this endpoint. Open-ended interview data will be tabulated, thematically coded and summarized by randomization group.

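### The only concordance summary named compares each woman's totals, so a stickered day with no opening can be cancelled by an extra opening on another day

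*Protocol*

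**What the plan says.** Section 3.1 lists concordance between opening-event data and self-report as the third of four primary objectives. For the active-device groups, section 10.5.2 says that the "analysis will include the following" and then names one item: "the proportion of participants whose number of events per signal data equals, exceeds, or is lower than the number of events per diary data". It adds: "No formal testing will be performed on this endpoint".

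Both sources are dated. Section 2.4 says that the device "provides a date and time stamp of when these occurred". Section 4.1 has the woman "place the sticker on the appropriate day of the week on a study provided diary card".

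The protocol expects openings that are not linked to a sticker. Section 2.5 plans a pretest algorithm for curiosity events, defined as "openings without taking any products". Section 7.4 lists such events, by the woman or by others, among the behaviors to assess. Section 13.5 worries about repeated openings out of curiosity. Section 10.5.2 does not mention the algorithm.

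**The concern.** Equal totals do not show that the two sources agree. A sticker placed on a day without an opening lowers the device total relative to the diary, and a curiosity opening on another day raises it again. A woman with both can be classed *equals* or *exceeds*, although her diary claims days on which the bag stayed shut. In the other direction, a woman who opened the bag and placed a sticker every day is classed *exceeds* as soon as one extra opening is recorded.

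Sections 2.2, 2.3 and 2.6.2 give inflated self-report as the reason for an objective measure. Extra openings push the totals in the direction that hides inflation. No test is planned, so this summary is itself the result that would inform the use of Wisebag in the VOICE ancillary study (section 2.5).

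**Working it through.** The protocol states no concordance or precision figure, so there is none to reproduce. The 1:2:2 split of 50 gives 10, 20 and 20, hence 40 women with an active device.

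**1. One woman.** Let the daily openings over 14 days be 1,1,1,1,0,1,1,2,1,0,1,2,1,1, with a sticker on every day. The openings sum to 14, the stickers to 14, and the class is *equals*. By day, only 12 of 14 agree: two stickered days had no opening.

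**2. Many women.** The following are assumptions and are not in the protocol:
- the diary shows 14 stickers;
- on each day the bag is opened for a sticker with probability 0.8;
- curiosity openings are Poisson with mean λ per day, and none are removed before counting.

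Let M ~ Binomial(14, 0.2) be the days without a sticker opening and E ~ Poisson(14λ) the curiosity openings. The device total is 14 − M + E. The class is *equals* if E = M, *exceeds* if E > M and *lower* if E < M. Summing over M gives:

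| λ | equals | exceeds | equals or exceeds | lower |
|---|---|---|---|---|
| 0.02 | 7.4% | 1.7% | 9% | 91% |
| 0.05 | 11.4% | 5.6% | 17% | 83% |
| 0.1 | 16.0% | 15.4% | 31% | 69% |
| 0.2 | 18.0% | 40.2% | 58% | 42% |

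Of 40 women, that is about 4, 7, 13 and 23 classed *equals* or *exceeds*. Under this model 0.8^14 = 4.4% of women made a sticker opening on all 14 days, so not every woman in these classes has a hidden gap.

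**3. Women with a gap.** A stickered day has no opening at all with probability r = 0.2·exp(−λ), so P(at least one such day) = 1 − (1 − r)^14, which is 95.3%, 94.8%, 93.9% and 91.8%. A woman classed *lower* must have such a day. The share of women with a gap whom the totals fail to class *lower* is therefore [P(gap) − P(lower)] / P(gap):
- λ = 0.02: (95.3 − 91.0)/95.3 = 5%
- λ = 0.05: (94.8 − 83.0)/94.8 = 12%
- λ = 0.1: (93.9 − 68.6)/93.9 = 27%
- λ = 0.2: (91.8 − 41.8)/91.8 = 54%

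With fewer missed days, cancellation is easier. If extra openings fall only on days already opened, the same shares are 11%, 26%, 46% and 72% when 10% of days are missed, and 17%, 37%, 60% and 84% when 5% are missed.

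**4. Fully adherent, honest women.** Here M = 0 and P(*exceeds*) = 1 − exp(−14λ) = 24%, 50%, 75% and 94% for the four values of λ. Day-level matching gives full agreement for all of them.

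**5. Practice session.** Table 1 has the woman "Practice opening/closing the bag and placing a study sticker on their diary card". For a perfect 14-day user:
- one counted opening and one counted sticker give 15 against 15, *equals*;
- one opening and no sticker give 15 against 14, *exceeds*;
- two openings and one sticker give 16 against 15, *exceeds*.

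The protocol does not say how many practice openings are made or whether practice events are kept.

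**6. Counting period.** The diary is two weekly cards. Section 7.2 sets the exit at Day 14 "with an allowable visit window of plus or minus 3 days", hence Day 11 to Day 17, and later attenders may still complete procedures during accrual. Table 2 refers to a download of two weeks of data, but section 10.5.2 does not tie the two counts to one window.

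**The case against.** The strongest case on the other side has four parts.

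*The list is open, and a statistical analysis plan may add day-level tables.* This is true, but the measure that is named remains the stated summary for a primary objective, and its weakness is not a matter of missing detail.

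*The curiosity algorithm may clean the counts.* If it is applied first and works well, most of the problem goes away. Section 10.5.2 does not say that it is applied; equally, nothing shows that raw openings will be counted.

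*The three classes are directional and carry no threshold or decision rule, in an exploratory pilot with about 40 active devices.* This stands, and it limits the severity.

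*The size is unknown.* This also stands: at 80% opening, *equals* or *exceeds* runs from 9% to 58% across the assumed curiosity rates, so no single figure should be quoted.

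A reader might infer three stronger points that the protocol does not support:
- Practice openings need not make honest women discordant, because the same session places a sticker. They do so only if counted practice openings outnumber counted practice stickers.
- The device and diary periods need not differ, given the two-week download in Table 2. They may differ for exits away from Day 14.
- The dated information is not thrown away. Sections 11.1 and 11.2 keep all data-file versions and treat diary data as source documents.

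**Conclusion.** The concern holds for the named measure. A comparison of totals can class a woman as *equals* or *exceeds* although some stickered days had no opening, and it classes an honest, fully adherent woman as *exceeds* after any uncancelled extra opening. The size rests on assumed rates of missed days and curiosity openings, on fully stickered diaries and on no prior cleaning of events. It is small if curiosity openings are rare and large if they are common. Practice openings and unequal periods are possible additions on which the protocol is silent or incomplete; they are not established errors. Severity is moderate: the endpoint is primary but descriptive and untested, and the retained data allow a better summary.

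**What to change.** In section 10.5.2, make day-level agreement the main concordance summary:
- For each woman and day, cross-classify at least one opening (yes/no) by sticker (yes/no).
- Report, for online and offline separately, overall agreement, the proportion of stickered days with an opening, and the proportion of opened days with a sticker.
- Use intervals that allow for repeated days within a woman, for example by resampling women.
- Fix one common window for both sources, such as Day 1 to the earlier of Day 14 and the day before exit, and exclude enrolment- and exit-visit openings and stickers.
- State whether the curiosity-event algorithm is applied first. This still matters by day, because a curiosity opening on a missed day would otherwise count as agreement.
- Keep the comparison of totals as a supplement.

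The cost is a change of wording, light programming and a day cut-off rule for openings near midnight. Calendar dates on the diary cards would make the matching easier. No new procedure or additional participants are needed.

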3 OBJECTIVES

3.1 Primary Objectives

- To compare the on-site technical performance of the “offline” and “online” functionalities of Wisebag
- To assess the success of attempted blinding of the “dummy” vs. active (“online” or “offline”) Wisebag
- To measure the concordance between Wisebag opening-event data (both “online” and “offline”) and self-reported data.
- To explore the feasibility and acceptability of Wisebag use by participants

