10.3 Primary Study Hypotheses

This is primarily an exploratory descriptive study that is not designed to test a hypothesis. However, the objectives of the study are based on the assumption that the "active" Wisebags will successfully and accurately record opening events, and will be acceptable for use by

women in the study, and that women will not be able to distinguish between an active and dummy Wisebag.

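### The one concordance summary named in Section 10.5.2 discards the size of the signal–diary mismatch, so within that result scattered small loss and large loss can look the same

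*Protocol*

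**What the plan says.** Section 3.1 of the Protocol makes concordance a primary objective: "To measure the concordance between Wisebag opening-event data" and self-reported data. Section 10.2 describes the outcome as the accuracy of the signal, online versus offline, judged against the diaries.

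Section 10.5.2 says concordance will be "summarized for participants assigned to the active device groups" and that the "analysis will include the following". One item then follows: "the proportion of participants whose number of events per signal data equals, exceeds, or is lower than the number of events per diary data". The paragraph closes with "No formal testing will be performed on this endpoint". No size of difference, ratio or tolerance is named there, in Section 4.2 or in Section 10.2.

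The design gives each woman about 14 daily events: "The target visit exit date will be 2 weeks (14 days) from the enrolment date" (Section 7.2, window plus or minus 3 days). On group sizes, Section 4.1 says: "Approximately 50 participants will be randomized to the 3 study arms in a 1:2:2 ratio".

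**The concern.** The named summary uses only the sign of signal minus diary. That has two effects.

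- **Size is lost.** One missed opening and fourteen missed openings fall in the same class. Section 2.1 of the Protocol reports effectiveness by adherence bands of above 80%, 50–80% and below 50%. Recording 13 of 14 openings is 93%, in the top band; recording 0 of 14 is in the bottom band. The summary merges them.
- **Agreement is strict.** One missed opening in two weeks moves a woman out of the equal class, so a device that records nearly everything can still show poor agreement.

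The pilot is meant to inform whether Wisebag enters a larger VOICE ancillary study (Sections 2.4 and 2.5). No test is planned on this endpoint, so the descriptive summary is the whole result. If it is read alone, minor scattered loss and serious loss could lead to the same conclusion.

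**Working it through.** **Inputs from the Protocol.** About 50 women at 1:2:2 (Section 4.1). Concordance in the active groups only, and three classes by sign (Section 10.5.2). Follow-up of 14 days, window 11 to 17 (Section 7.2).

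**Assumptions, not in the Protocol.** One diary event per day, no dropout, no extra openings, and independent loss where a loss probability is used. The Protocol gives no recording rate, so a range is shown.

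**1. The plan's own figure.** 50 × 1/5 = 10 and 50 × 2/5 = 20, giving 10/20/20 as in Table 3. The active groups therefore hold 40 women and 40 × 14 = 560 expected diary events. The Protocol states no precision or concordance figure to reproduce.

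**2. Same split, different loss.** Let 20 of the 40 women fall short of the diary and 20 match it. The planned result is 50% equal, 0% above and 50% below in every row.

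| Shortfall per affected woman | Events lost | Share of 560 | Mean signal minus diary |
|---|---|---|---|
| 1 | 20 | 3.6% | −0.5 |
| 3 | 60 | 10.7% | −1.5 |
| 7 | 140 | 25.0% | −3.5 |
| 14 (nothing recorded) | 280 | 50.0% | −7.0 |

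The last row is 280/20 = 14 times the first. Leaving out bags that recorded nothing, the third row is still 140/20 = 7 times the first.

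**3. Exact equality.** If each opening is recorded with probability p, the chance of equality over k days is p^k.

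| p | k = 11 | k = 14 | k = 17 |
|---|---|---|---|
| 0.99 | 89.5% | 86.9% | 84.3% |
| 0.98 | 80.1% | 75.4% | 70.9% |
| 0.95 | 56.9% | 48.8% | 41.8% |
| 0.90 | 31.4% | 22.9% | 16.7% |

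At p = 0.95 and 14 days, 1 − 0.488 = 51.2% of women are below the diary although 5% of events are lost. The equal share also drifts with the exit date inside the allowed window.

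**4. With 20 women per arm** (20,000 simulated runs, 14 openings each). Scenario A is 5% independent loss; in scenario B half the devices are dead.

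| | Share of women below diary (95% range) | Share of openings lost (95% range) |
|---|---|---|
| A | 51% (30–75%) | 5.0% (2.5–7.9%) |
| B | 50% (30–70%) | 50% (30–70%) |

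The planned proportion does not separate the scenarios. The share lost does.

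**5. Sensitivity to extra openings.** With 10% loss and an average of 1.4 extra openings per woman (both assumed), about 38% of women are below the diary, 37% above and 26% equal. Without extra openings the 10% row gives 100 − 22.9 = 77.1% below. The 51% and 50% above are therefore illustrations, not predictions.

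**The case against.** Four points can be made on the other side.

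- **The list is open.** A reader might infer that concordance will be reported only as three proportions. The text does not say so: "analysis will include the following" excludes nothing, and an analysis plan that is not shown may add summaries. This stands, and the point is limited to the only summary the Protocol names. It remains a point because that one summary is a weak choice for a primary objective.
- **Dead bags are seen elsewhere.** A reader might infer that the study could not tell a nearly perfect device from one that lost half its data. The documents do not support that. The performance analysis in Section 10.5.2 counts download, wireless, battery and signal faults in each active group, and heartbeat, opening-event and diary data all belong to the technical performance endpoint (Section 4.2). Half the devices being dead would be prominent there. What remains is partial or scattered loss. The heartbeat indicates battery function (Section 2.4), so a working device that misses some openings may not be counted as a failure.
- **Below the diary is not the same as device loss.** Sections 2.2, 2.3 and 2.6.2 start from the premise that self-report is inflated, so a shortfall may come from the diary. This stands. Direction is informative, and adding size does not separate the two causes.
- **The study is descriptive.** Section 10.3 says: "This is primarily an exploratory descriptive study that is not designed to test a hypothesis". No threshold depends on these proportions, and the counts can be summarised again later. That limits the harm but leaves the named summary uninformative about size.

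**Conclusion.** The concern holds in a limited form. The only concordance summary named in Section 10.5.2 discards the size of the mismatch and demands exact equality over about 14 events. The same 50/50 split can arise from 3.6% or 25% of events missing when every bag recorded something, and from 50% when the affected bags recorded nothing. The loss of size follows from the definition alone. The percentages rest on 14 diary events per woman, no dropout, no extra openings and, where stated, independent loss.

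The documents do not support reading this as a study unable to detect failed bags, or the lower class as a measure of device loss. The weakness lies within the concordance result and mainly concerns partial or scattered mismatch. No error rate or sample size is affected. A small change of wording before analysis is worthwhile.

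**What to change.** In the concordance paragraph of Section 10.5.2, keep the three-way split and add the following, for online and offline separately:

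- each participant's signed difference (signal minus diary), and the signal-to-diary ratio where the diary count is above zero, both summarised by median, quartiles and range;
- a plot of the individual values;
- a class for agreement within one event;
- bags that recorded nothing, shown separately.

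Do not use normal-theory limits of agreement. With 10 of 20 women at 0 and 10 at −14, the mean is −7 and the SD is 7 × √(20/19) = 7.2. The limits are then −7 ± 1.96 × 7.2, about −21 to +7, while in that scenario differences can only lie between −14 and 0. The ratio is restricted because it is undefined when the diary count is zero.

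The text should also say that a signal count below the diary may reflect missed recording or diary over-reporting. The cost is a few sentences and a slightly less simple headline. The counts are already collected, so no data, visits or participants are added.
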